**2. PARTICIPANTS:**

a. RECRUITMENT

Participants will be recruited at 2-3 months of age through Pediatric Associates, PSC, a pediatrician practice that has 3 locations in northern Kentucky. If adequate enrollment cannot be achieved through Pediatric Associates, an amendment will be submitted to expand recruitment

to include daycares, Sona system (i.e., student participants can enroll if they have a child meeting study inclusion criteria), and internet and social media sites for our research lab (i.e., The Healthy Kids Lab).

1) Number of participants

The study will enroll 40 total participants. Twenty participants will be randomized to receive the study treatment and 20 participants will be randomized to the control group.

(b) Rationale

This number of participants was determined based on the number of participants feasible to enroll as part of a pilot study while still generating enough data regarding treatment feasibility.

2) Inclusion and exclusion criteria

Participants will be infants aged 3-9 months and their families ( $n = 40$ ). Infants with both normal and elevated weight-for-length will be enrolled. Inclusion criteria include 1) infant has not previously been introduced to complementary foods (i.e., any food besides formula or breastmilk), 2) infant does not have a known developmental delay, 3) infant does not have impaired fine or gross motor skills (which would impact ability for self-feeding), 4) infant does not have a condition currently impacting their feeding and eating, 5) infant born at  $\geq 38$  weeks gestation, 6) infant current weight-for-length  $\geq 10^{\text{th}}$  percentile (Infants with suboptimal growth will be excluded due to potential safety implications of modifying eating and feeding styles of infants with growth difficulties), and 7) parent is a fluent English speaker (because this is the language the intervention will be delivered in).

3) Vulnerable participants

(a) Vulnerability

All study participants will be children less than 1 year old.

(b) Rationale

The objective of the current study is to test an intervention for healthy infant feeding. Therefore, all participants are required to be infants.

(c) Confirmation

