#### **4. DATA ANALYSIS:**

Aim 1 (Determine the feasibility of the *HSF* intervention and family satisfaction with the treatment) will be explored using descriptive analyses. We will calculate the average number of treatment sessions attended and the percentage of participants attending 2 (67%) and 3 (100%) of the sessions. Additionally, we will calculate the percentage of caregivers who either "somewhat agree" or "strongly agree" that the intervention is appropriate, timely, helpful, and satisfactory as assessed by the Treatment Satisfaction Survey. Qualitative comments on the Treatment Satisfaction Survey will also be reviewed to identify themes regarding additional information to include in the intervention, what information was most helpful, what caregivers would like to see changed about the intervention, and what they would like to see stay the same.

Aim 2 (Examine the impact of the *HSF* intervention on growth trajectories, appetite regulation, and diet at post-treatment) will be explored through group comparisons between the control and treatment groups on weight-for-length scores, subscale scores of the *BEBQ*, and number of fruits and vegetables consumed in the last week as assessed on a food frequency questionnaire. Prior to between group comparisons, potential differences between the control and treatment group on key sociodemographic and baseline variables (e.g., gender, baseline weight-for-length, household income, caregiver education level) will be explored to confirm the

effectiveness of randomization to treatment condition. A series of Analysis of Variance (ANOVA) will be computed to examine whether the control and treatment groups differ on outcome variables. If missing data are present, we will also consider an alternative analyses using a repeated measures model with maximum likelihood estimation to examine group differences on outcome variables, which will allow inclusion of all participants despite missing data.

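### The optional missing-data model is to be fitted by maximum likelihood in at most 40 infants, which slightly understates standard errors, and its contrast is not named

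*Protocol*

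**What the plan says.** The main Aim 2 analysis in the protocol (4. DATA ANALYSIS) is ANOVA: "A series of Analysis of Variance (ANOVA) will be computed to examine whether the control and treatment groups differ on outcome variables". The fallback is a "repeated measures model with maximum likelihood estimation to examine group differences on outcome variables". It is conditional and discretionary: "If missing data are present, we will also consider an alternative analyses using a repeated measures model with maximum likelihood estimation". Its purpose is given as "to examine group differences on outcome variables, which will allow inclusion of all participants despite missing data". The clause names an estimator but no visit, contrast, group-by-visit term, covariance structure, degrees-of-freedom method or handling of baseline. The same section describes Aim 2 as impact on "growth trajectories, appetite regulation, and diet at post-treatment".

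On size, section 2. PARTICIPANTS states "The study will enroll 40 total participants", 20 per arm, and the rationale is feasibility: "This number of participants was determined based on the number of participants feasible to enroll as part of a pilot study". Neither document states a significance level, effect size, SD, correlation between visits or expected dropout.

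The SAP repeats the ANOVA and has no missing-data method.

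**The concern.** The clause raises two separate issues.

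The first is the estimator. Maximum likelihood divides the residual sum of squares by the number of infants, not by the residual degrees of freedom, so the variance is biased downward. The bias is negligible in a large trial but not quite negligible in 40 infants or fewer. A normal reference distribution, if the software uses one, adds to it. Intervals would be somewhat too narrow and p-values somewhat too small.

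The second is the target. Outcomes are taken at two study visits, and the first precedes randomisation, so its expected group difference is zero. The phrase about group differences does not say which term will be read. A 9-month contrast or a group-by-visit interaction estimates the full effect; a group main effect over both visits does not. Without a named contrast, the choice stays open until the data have been seen.

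**Working it through.** The plan gives no power or precision figure to reproduce. The only sum to check is the allocation, 20 + 20 = 40, which agrees.

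**Inputs from the documents.** At most 40 infants (protocol, 2. PARTICIPANTS). Two study visits, at 3 and 9 months, for anthropometrics, BEBQ and the food frequency questionnaire (protocol, 3. RESEARCH-RELATED ACTIVITY, Data collection tools). Assignment after baseline measures (same section, Participant cohorts). No complementary foods before entry (2. PARTICIPANTS, Inclusion and exclusion criteria).

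**Assumptions.** Two-sided 5% level and 0 to 20% dropout, so n = 40 to 32 infants with a 9-month value. The model is triggered only by missing data, so n = 40 is a limiting case.

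**Step 1: standard error.** With p mean parameters, the ratio of the ML standard error to the unbiased one is √((n − p)/n). Take p = 2 for a plain two-group comparison and p = 3 for a baseline-adjusted one. With ν = n − p, the true size is

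- normal cut-off: 2·P(t_ν > 1.96 × ratio)
- t cut-off: 2·P(t_ν > t_ν,0.975 × ratio)

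| p | n | SE ratio | Size, normal cut-off | Size, t cut-off |
|---|---|---|---|---|
| 2 | 40 | √(38/40) = 0.975 | 6.4% | 5.6% |
| 2 | 32 | √(30/32) = 0.968 | 6.7% | 5.7% |
| 3 | 40 | √(37/40) = 0.962 | 6.7% | 5.9% |
| 3 | 32 | √(29/32) = 0.952 | 7.2% | 6.1% |

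Standard errors are therefore 2.5% to 4.8% too small. A simulation of the two-visit ML model agrees: with unstructured covariance, 20 per arm, 0 to 30% missing completely at random, correlation 0.3 to 0.7 and 8,000 runs per setting, size with a 1.96 cut-off was 6.0% to 7.2%. REML with a 1.96 cut-off still gives 5.7% at n = 40 (p = 2), so the degrees-of-freedom method matters as well as the estimator.

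**Step 2: contrast.** Let the true group difference be 0 at 3 months and δ at 9 months. With complete data and equal variances, a group main effect has expectation (0 + δ)/2 = 0.50δ. With missing 9-month values, the 3-month visit gets more weight. At zero correlation and 16 of 20 per arm remaining, the expectation is 16/(20 + 16) = 0.44δ. Under random-intercept weighting with correlation 0 to 0.7, it is 0.46 to 0.47δ at 10% missing, 0.41 to 0.44δ at 20% and 0.37 to 0.41δ at 30%. The 9-month contrast from a group-by-visit model has expectation 1.00δ.

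**Step 3: fruit and vegetable count.** Eligibility implies a 3-month count of zero for every infant. A variance pooled over visits would then be half the 9-month variance, giving a 9-month standard error of √0.5 = 0.71 of its true value. With the ML factor and a 1.96 cut-off, size is 2·P(t_38 > 1.96 × √(0.5 × 38/40)) = 18%. This comes from the covariance choice, not from ML. An unstructured covariance does not help here, because a zero-variance visit makes it singular.

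**The case against.** The strongest reply is that little depends on this clause. ANOVA is the main analysis and has neither problem. The model is something the team will consider, not something it commits to, and Aim 2 is exploratory in a pilot sized by feasibility. That stands and keeps the severity low.

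It is also fair to say that the bias due to ML alone is small, about 0.6 to 1.1 percentage points of size with t quantiles. The rest depends on a normal cut-off that neither document specifies, and the phrase maximum likelihood may be loose wording that includes REML. All of that stands too. As written, though, the protocol names ML, and the correction costs almost nothing.

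A reader might infer that the plan would halve the treatment effect and so probably miss a real one. The documents do not support that. They nowhere say that the group term averages over visits. The aim is set at post-treatment, and anthropometrics are described as collected for pre-post analysis; both point towards a 9-month or change contrast. Exactly half also needs complete data and equal variances at the two visits. No effect size, SD or correlation is given from which a loss of power could be claimed. What remains is that the contrast is not named.

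**Conclusion.** The point holds as a low-severity correction. The one missing-data model in either document specifies an estimator that, uncorrected in 32 to 40 infants, understates standard errors by about 2.5% to 5%. At an assumed two-sided 5% level, that means a true size of 5.6% to 6.1% with t quantiles and 6.4% to 7.2% with a normal cut-off. Separately, the contrast is unspecified. Reading a group main effect over both visits would give about half the effect, or less with missing 9-month data, but the stated aim favours the 9-month difference. The significance level, dropout and correlations used here are assumptions. The main ANOVA is not affected.

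**What to change.** Replace the clause for weight-for-length and BEBQ scores with: a repeated measures model fitted by REML with Kenward-Roger degrees of freedom and unstructured covariance, 3-month means constrained equal across arms, reporting the treatment-minus-control difference at 9 months with its 95% CI.

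For the fruit and vegetable count, analyse the 9-month value only, because the 3-month value should be zero for all infants and the model above could not be fitted. Carry both statements into the SAP.

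The cost is a few sentences and a software option. Relative to ML with a normal cut-off, intervals widen by the factor (t_ν,0.975/1.96)/ratio. This runs from (2.024/1.96)/0.975 = 1.06 (p = 2, n = 40) to (2.045/1.96)/0.952 = 1.10 (p = 3, n = 32), so about 6% to 10%. If t quantiles would have been used anyway, the widening is 1/0.975 to 1/0.952, about 3% to 5%.

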## **6. ADDITIONAL DOCUMENTATION:**

Not applicable.

College of Arts and Sciences
Department of Psychology
University of Cincinnati
Cincinnati, OH, 45221

Official Title: Healthy Start to Feeding Pilot Trial

Brief Title: Healthy Start to Feeding Intervention

NCT Number: NCT03597061

Document Date: 7/9/2018

Date Uploaded: 6/24/21

Document: Statistical Analysis Plan

Statistical Analysis Plan

Primary Aim (Examine the impact of the HSF intervention on growth trajectories, appetite regulation, and diet at post-treatment) was explored through group comparisons between the control and treatment groups on weight-for-length scores, subscale scores of the BEBQ, and number of fruits and vegetables consumed in the last week as assessed on a food frequency questionnaire. Prior to between group comparisons, potential differences between the control and treatment group on key sociodemographic and baseline variables (e.g., gender, baseline weight-for-length, household income, caregiver education level) were explored to confirm the effectiveness of randomization to treatment condition. A series of Analysis of Variance (ANOVA) were computed to examine whether the control and treatment groups differed on outcome variables.

Secondary Aim (Determine the feasibility of the HSF intervention and family satisfaction with the treatment) was explored using descriptive analyses. We calculated the average number of treatment sessions attended and the percentage of participants that attended 2 (67%) and 3 (100%) of the sessions. Additionally, we calculated the percentage of caregivers who either “somewhat agree” or “strongly agree” that the intervention was appropriate, timely, helpful, and satisfactory as assessed by the Treatment Satisfaction Survey. Qualitative comments on the Treatment Satisfaction Survey were also reviewed to identify themes regarding additional information to include in the intervention, what information was most helpful, what caregivers would like to see changed about the intervention, and what they would like to see stay the same.
